7.2 Assessing, Recording, and Analyzing Efficacy Parameters

VA, PD, and wavefront error (total and higher order) will be measured at Visit 1 (Screening/Baseline), Visit 2 (Treatment), and Visit 3 (Treatment) as described in [Section 4.1](#).

[REDACTED]

[REDACTED] to the set of PD, BCDVA, DCNVA, and wavefront error measurements). Subject will sit in the exam chair facing directly at the illuminated chart during the acclimation period and for all assessments. Room lights may be turned on for the scheduled remaining safety assessments (e.g., conjunctival hyperemia, AEs, subject questionnaire, etc.). The subject will be in the same room for all assessments, and every effort will be made to have the same person perform the measurements at all visits.

7.2.1 *Visit 1 (Screening/Baseline)/Day 1*

Individuals who are potential subjects are identified by the study center to schedule the Screening Visit. The Screening Visit should occur the same day as the Baseline Visit, where the dose of study treatment is given.

Once a subject arrives at the study center, a member of the study center staff will interview the individual as to their qualifications for participation in the study, and if the subject wishes to continue, the informed consent form is signed, and a subject identification number is assigned.

If the subject wears soft contact lenses, they must be removed for at least 1 hour prior to ophthalmic assessments. If the subject wears hard gas-permeable contact lenses, they must be removed for at least 8 hours prior to testing.

The start of screening includes an explanation of the study, a medical and ophthalmic history, demographics, and a review of prior/concomitant medications. During this time, eligibility for [REDACTED] must be determined first. Then, ophthalmic and non-ophthalmic criteria ([REDACTED]) shall be determined and only eligible subjects will continue. This shall be followed by a urine pregnancy test for females of childbearing potential [REDACTED] and HR/BP ([REDACTED] [REDACTED]).

Prior to further screening, the subject must be asked to complete the subject questionnaire. Subjects should then have their refraction confirmed using the High contrast distance chart as detailed in the Study Procedures Manual. Following a [REDACTED] [REDACTED], subjects shall be assessed in each eye for PD and for mLCVA before and during illumination of the [REDACTED] [REDACTED] ([REDACTED])

[REDACTED]
[REDACTED]
[REDACTED]
[REDACTED]

[REDACTED] OD shall be the study eye. Investigators should frequently remind subjects to blink between visual acuity assessments.

The study eye of the subject must meet [REDACTED] in order for the subject to not screen fail.

Before further screening criteria, the following assessments shall be performed to establish baseline values:

- mHCVA, pLCVA, and mesopic high-contrast DCNVA
- [REDACTED] corneal topography measurements under [REDACTED], and other data captured
- Conjunctival hyperemia, assessed visually with a grading scale (0–3) using images from the CCLRU (Investigators are cautioned to appropriately note all observations of conjunctival hyperemia on the biomicroscopy eCRF at screening)
- Slit lamp biomicroscopy

The subject must also meet dry eye Exclusion Criterion #13 to be included in the study at the determination of the investigator. Specifically, subjects with undiagnosed dry eye may undergo a dry eye test (one of the below):

- a. TearLabs osmolarity test (> 308 mOsm/L in either eye or an inter-eye difference ≥ 10 mOsm/L)
- b. Corneal fluorescein staining (\geq grade 2 in the inferior or \geq grade 1 in the central zone using the National Eye Institute scale)
- c. Tear break-up time of < 5 seconds

Final screening must include IOP measurement (using a Tono-Pen) and ophthalmoscopy.

With the subject passing all eligibility criteria, the Screening Visit becomes the Baseline Visit. The subject will then be assigned a randomization number and randomized into the study.

Through the screening process at Visit 1, all assessments will have been completed as defined in [Table 2](#). A summary of the screening process is outlined in [Appendix 5](#).

If the subject meets all eligibility criteria, they will be randomized to a treatment group. If a subject fails the screen, they can return for a rescreening (signing a new informed consent and assigning a new subject number) at the investigator's discretion.

Site personnel will then demonstrate the proper instillation technique to the subject. The subject at home should be in a seated position and should tilt his or her head backward for administration of the study medication. The bottle of study medication should be held at an almost vertical position above the eye while the lower eyelid is pulled down gently, and 1 drop is placed into the conjunctival cul-de-sac. The tip of the bottle should not touch the eye. After a drop is instilled in each eye, the subject should keep the eyes gently closed for approximately 30 seconds. After successful instillation of the drop in each eye, the subject should carefully empty any remaining contents as directed.

The subject is given their medication dropper bottles in a kit and instructions regarding when to administer the eye drop (8PM to 10PM QD), and when to return to the clinic. All treatments will be administered OU.

The first dose of study medication will be taken at 8PM to 10PM on the evening of the Baseline Visit (Day 1). If the subject wears contact lenses, they must be removed prior to dosing and not replaced until the next morning at the earliest.

Each subsequent evening of dosing, the subject will administer 1 drop to each eye from a single new unit-dose bottle and close the eyes gently for 30 seconds, then empty the

remaining contents and store the opened bottle in the foil pouch and place it in the medication box for return to the study site at Visit 2 (Day 8). Each subsequent evening of dosing (approximately 24 hours between doses), the subject will follow the same procedures.

The subject should be instructed to contact the Investigator should AEs of concern occur (e.g., shortness of breath, fainting, etc.). If the event is life-threatening, then the subject should go to the emergency room.

7.2.2 *Visit 2 (Treatment)/Day 8 (± 1 day)*

If the subject wears contact lenses, [REDACTED] prior to ophthalmic assessments. At Visit 2, the medication box, complete with opened bottles and any unopened study medication, and diary will be returned to the study site where the site will account for opened and unopened study medication and the study medication box will be re-dispensed with the unopened medication.

The subjects will be asked if they had any problems with their eyes since the last visit, and if there have been any changes in their medical condition or concomitant medications since their last visit. *Any adverse changes in the condition of the subject are recorded as an AE.*

In addition, at Visit 2 subjects shall have the following assessments, as defined in [Table 2](#):

- Females of childbearing potential must take a urine pregnancy test.
- Subject must have HR and BP assessments.
- Subject shall be assessed using the subject questionnaire.
- Pupil diameter
- Subject shall be assessed for mLcVA, mHCVA, pLCVA and DCNVA (mesopic, high-contrast conditions) as mentioned in [Section 4.1](#).
- OPD Scan measurements (for those sites with OPD Scan III), wavefront aberrometry (total and higher-order RMS) and corneal topography measurements under mesopic conditions, and other data captured
- Eye redness (conjunctival hyperemia) will be assessed visually with a grading scale (0-3) using images from the CCLRU.
- Subject will have an IOP assessment.

7.2.3 *Visit 3 (Treatment)/Day 15 (± 1 day)*

During the second week of treatment, subjects will continue to administer 1 drop of study medication OU every night using a new bottle for each dose, then emptying the remaining contents of that bottle, return the opened bottle to its foil pouch and place it in the medication box for return to the study site at their next visit.

If the subject wears contact lenses, they must be removed for a minimum of 8 hours prior to ophthalmic assessments. At Visit 3, the subject will bring their used dropper bottles with any unused medications and diary with them for purposes of drug accountability. The last day of study treatment is the day before Visit 3; no further study medication will be dispensed at Visit 3.

The subjects will be asked if they had any problems with their eyes from the last visit, and if there have been any changes in their medical condition or concomitant medications since their last visit. ***Any adverse changes in the condition of the subject are recorded as an AE.***

In addition, at Visit 3 subjects will have the following assessments, as defined in [Table 2](#):

- Females of childbearing potential must take a urine pregnancy test.
- Subject must have HR and BP assessments.
- Subject shall be assessed using the subject questionnaire.
- Pupil diameter
- Subject shall be assessed for mLcVA, mHCVA, pLCVA, and DCNVA (mesopic, high-contrast conditions) as mentioned in [Section 4.1](#).
- OPD Scan measurements (for those sites with OPD Scan III), wavefront aberrometry (total and higher-order RMS) and corneal topography measurements under mesopic conditions, and other data captured
- Eye redness (conjunctival hyperemia) shall be assessed visually with a grading scale (0-3) using images from the CCLRU.
- Subject shall be assessed using biomicroscopy.
- Subject must have an IOP assessment.
- Subject shall be assessed using ophthalmoscopy.

7.2.4 *Follow-Up Phone Call Visit 4*

Up to 3 days after Visit 3, subjects will be called and asked if they had any problems with their eyes from the last visit, including whether their eyes are red, and if there have been any changes in their medical condition or concomitant medications since their last visit.

Any changes in the condition of the subject are recorded as an AE.

If an AE/adverse reaction is unresolved at the time of the last visit or if a subject reports a worsening of symptoms, every effort should be made to follow up until the AE/adverse reaction is resolved or stabilized, the subject is lost to follow-up, or there is other resolution to the event.

7.2.5 *Unscheduled Visits*

An Unscheduled Visit may be any visit to the Investigator other than the specific visits requested in the protocol as possibly required for the subject's ophthalmic condition. The Investigator will perform all procedures necessary to evaluate the study participant at these visits and record any AEs in the eCRF.

As noted in [Section 4.9.4](#), every possible effort should be made by Investigators to assure that subjects who discontinue early from the study have a telephone follow-up that includes assessments of AEs, concomitant medications, and subject-evaluated conjunctival hyperemia.

7.2.6 *Visit Variation*

Visit 2 on Day 8 and Visit 3 on Day 15 may each be 1 day late. If the visit is late, the subject should be advised to take an additional dose from 1 of the 2 spare dropper bottles provided in the study medication box the night before the visit. The subject should then empty the remaining contents and return the opened bottle to its foil pouch and place it in the medication box for return to the study site at their next visit. The follow-up telephone call may occur up to 3 days after Visit 3.

8 ASSESSMENT OF SAFETY

8.1 Specification of Safety Parameters

The assessment of safety and tolerability is the secondary objective of this study. The assessment of safety will be evaluated by:

- Conjunctival hyperemia measured with CCLRU images using a 4-point scale (0-3) ([Appendix 6](#)).
 - None (0) = Normal; appears white with a small number of conjunctival blood vessel easily observed
 - Mild (+1) = Prominent, pinkish-red color of both the bulbar and palpebral conjunctiva
 - Moderate (+2) = Bright, scarlet red color of the bulbar and palpebral conjunctiva
 - Severe (+3) = Beefy red with petechiae, dark red bulbar and palpebral conjunctiva with evidence of subconjunctival hemorrhage
- Biomicroscopy of the anterior segment includes evaluation of cornea, conjunctiva, and anterior chamber. Fluorescein staining will be used.
- IOP is measured with the Tono-Pen.
- Ophthalmoscopy direct or indirect fundus exam without dilation includes optic nerve, macula, vessels, and periphery (note: Use of 90 D lens (indirect) is allowed).
- HR and BP are measured as per the site's normal equipment and procedures.
- AEs
- Brief subject questionnaire ([Appendix 3](#))

8.2 Assessing, Recording, and Analyzing Safety Parameters

The timing for recording safety parameters may be found in [Table 2](#).

8.3 Adverse Events and Serious Adverse Events

All AEs and SAEs that occur following consent and until the final study visit should be collected and recorded on the AE or SAE eCRF page. Only treatment-emergent adverse events/adverse reactions (TEAEs) will be summarized ([Section 9.3.5](#)).

All AEs/adverse reactions occurring during the study (i.e., once the subject has signed the informed consent/assent) **must** be documented, regardless of the assumption of causal relationship, on the respective eCRF. All TEAEs/adverse reactions must be documented from the time the subject receives the study medication until the subject's participation in the study has been completed. If a subject has ongoing AEs/adverse reactions at the time of study completion or discontinuation from the study, the ongoing AEs/adverse reactions **must** be followed-up and provided appropriate medical care until the signs and symptoms

have remitted or stabilized or until medical assessments have returned to acceptable or pre-study limits.

Documentation of AEs/adverse reactions includes start date and end date, severity, relationship to study medications, action(s) taken, seriousness, and outcome.

8.3.1 *Adverse Event Definitions*

The following definitions of terms apply to this section:

Adverse event. An AE is any untoward medical occurrence associated with the use of a study medication in humans, whether or not considered drug related. An AE can therefore be any unfavorable and unintended sign (including abnormal laboratory findings), symptom, or disease temporarily associated with the use of the study medication, whether or not related to the study medication. Study medication includes the investigational drug under evaluation and the comparator product or vehicle placebo that is given or administered during any phase of the study.

Medical conditions/diseases present before starting the investigational treatment are only considered AEs if they worsen after starting the investigational treatment. Abnormal test results constitute AEs only if they induce clinical signs or symptoms, are considered clinically significant, or require therapy.

The occurrence of AEs should be sought by open-ended questioning of the subject at each visit during the study. At each clinic assessment/visit, study personnel should ask the following question: “Have you had any problems since your last assessment/visit?”. AEs also may be detected when they are volunteered by the subject during or between visits or through study assessments.

Life-threatening AE or life-threatening suspected adverse reaction. An AE or suspected adverse reaction is considered “life-threatening” if, in the view of either the Investigator or Ocuphire, its occurrence places the subject at immediate risk of death. It does not include an AE or suspected adverse reaction that, had it occurred in a more severe form, might have caused death.

SAE or serious suspected adverse reaction. An AE or suspected adverse reaction is considered “serious” if, in the view of either the Investigator or Ocuphire, it results in any of the following outcomes:

- Death
- Life-threatening AE
- Inpatient hospitalization or prolongation of existing hospitalization
- Persistent or significant incapacity or substantial disruption of the ability to conduct normal life functions
- Congenital anomaly/birth defect

- Other medically important serious event

Important medical events that may not result in death, be life-threatening, or require hospitalization may be considered serious when, based upon appropriate medical judgment, they may jeopardize the subject and may require medical or surgical intervention to prevent one of the outcomes listed in this definition.

Treatment on an outpatient emergency basis that does not result in hospital admission, or a hospitalization that is elective or is a preplanned treatment for a pre-existing condition that is unrelated to the medication under study and has not worsened since the start of the study, is not considered an SAE.

Suspected adverse reaction means any AE for which there is a reasonable possibility that the drug caused the AE. For the purposes of Investigational New Drug (IND) safety reporting, “reasonable possibility” means there is evidence to suggest a causal relationship between the drug and the AE. Suspected adverse reaction implies a lesser degree of certainty about causality than adverse reaction, which means any AE caused by a drug.

Unexpected adverse event or unexpected suspected adverse reaction. An AE or suspected adverse reaction is considered “unexpected” if it is not listed in the IB or is not listed at the specificity or severity that has been observed; or, if an IB is not required or available, is not consistent with the risk information described in the general investigational plan or elsewhere in the current application, as amended. “Unexpected,” as used in this definition, also refers to AEs or suspected adverse reactions that are mentioned in the IB as occurring with a class of drugs or as anticipated from the pharmacological properties of the drug but are not specifically mentioned as occurring with the particular drug under investigation.

The study medication relationship for each AE/adverse reaction should be determined by the Investigator using these explanations:

- Not related
- Unlikely related
- Possibly related
- Probably related
- Definitely related
- Unknown

Unless the relationship is considered to be “Not related” or “Unlikely related” and there is any valid reason, even if undetermined, for suspecting a possible cause-and-effect relationship between the study medication and the occurrence of the AE, then the AE should be considered “related”.

If the relationship between the AE/SAE and the investigational product is determined by Ocuphire to be anything other than “Not related” or “Unlikely related” the event will be considered to be related to the investigational product for the purposes of expedited regulatory reporting.

Severity of an AE is defined as a qualitative assessment of the level of discomfort of an AE as is determined by the Investigator or reported to him/her by the subject. The assessment of severity is made irrespective of study medication relationship or seriousness of the event and should be evaluated according to the following scale:

- 1 = Mild: present, but not distressing, and no disruption of normal daily activity
- 2 = Moderate: discomfort sufficient to reduce or affect normal daily activity
- 3 = Severe: incapacitating, with inability to work or perform normal daily activity

A change in severity for a reported AE will require an end date for the previous severity and a new start and end date for the new severity. For example, a change in severity may go from mild to severe or from severe to moderate. In either case, the start or end times/dates should be recorded.

The term “severe” is used to describe the intensity of an event/reaction; the event/reaction itself may be of relatively minor medical significance (such as a severe headache). This is not the same as a “Serious” AE, which is based on a subject/event outcome or action criteria usually associated with events that pose a threat to the subject’s life or vital functions. “Seriousness” (NOT severity) serves as a guide for defining regulatory reporting obligations.

Action taken in response to an AE is coded as:

- Dose increased: An indication that a medication schedule was modified by addition; either by changing the frequency, strength, or amount.
- Dose not changed: An indication that a medication schedule was maintained.
- Dose reduced: An indication that a medication schedule was modified by subtraction, either by changing the frequency, strength, or amount.
- Dose interrupted: An indication that a medication schedule was modified by temporarily terminating a prescribed regimen of medication.
- Drug withdrawn: An indication that a medication schedule was modified through termination of a prescribed regimen of medication.
- Not applicable: Determination of a value is not relevant in the current context
- Unknown: Not known, not observed, not recorded, or refused

Additional other action taken:

- Concomitant medication
- Hospitalization

Outcome of an AE is coded as:

- Fatal: The termination of life as a result of an AE
- Not recovered/not resolved: One of the possible results of an AE outcome that indicates that the event has not improved or the subject recuperated
- Recovered/resolved: One of the possible results of an AE outcome that indicates that the event has improved or the subject has recuperated
- Recovered/resolved with sequelae: One of the possible results of an AE outcome where the subject recuperated but retained pathological conditions resulting from the prior disease or injury
- Recovering/resolving: One of the possible results of an AE outcome that indicates that the event is improving
- Unknown: Not known, not observed, not recorded, or refused

In previous clinical studies of Nyxol, the most frequently reported AE was conjunctival hyperemia.

In the present study, any increase of 2 units in conjunctival hyperemia between consecutive visits is considered an AE.

Investigators are cautioned to use the appropriate verbatim term on the AE form to describe this observation:

- Redness related to instillation that is transient (i.e., is no longer present 2 hours after instillation) = “conjunctival erythema upon instillation”
- Redness that is NOT transient (i.e., is present \geq 2 hours after instillation) = “conjunctival hyperemia”

Expedited reporting of Serious and Unexpected Adverse Events: All SAEs (related and unrelated) will be recorded following subject signature of the informed consent/assent and until the Follow-up Visit. Any SAEs “suspected” to be related to the study medication and discovered by the Investigator at any time **after** the study should be reported.

Any SAE that occurs must be reported to the CRO within 24 hours of its occurrence or within 24 hours of learning of its occurrence. Recurrent episodes, complications, or

progression of the initial SAE must be reported to the CRO as follow-up to the original episode within 24 hours of the Investigator receiving the information. Information about all SAEs will be collected and recorded on the SAE form. All pertinent medical records and information collected during the treatment and follow-up of the subject should be maintained at the site with a copy emailed to [REDACTED]. The Investigator must assess the SAE relationship and complete the SAE form. The CRO may request additional information. Follow-up information (e.g., discharge summary) will be retained in the subject's chart and a copy will be emailed to [REDACTED]. In addition, all SAEs should be recorded on the AE eCRF page with the serious question marked "Yes".

It is the Investigator's responsibility to notify the approving IRB of any SAEs on a timely basis as instructed by Ocuphire following Ocuphire's determination of causality. All subjects who experience an SAE should be followed clinically and undergo the appropriate diagnostic evaluations until stabilization or resolution of the event. Ocuphire will report all SAEs to the FDA on the appropriate schedule depending if the event is drug related or not drug related, expected, unexpected (based on the available information in the IB).

Any death occurring during the study and follow-up period must be reported as an SAE. For any death occurring through the end of the study, regardless of the degree of relationship to study medication, the SAE resulting in the death must be reported to the CRO. A death occurring after completion of the study, including the Safety Follow-up Visits, that is not reasonably associated with study medication administration does not require completion of the SAE form.

[figure not shown]
8.3.2 *Follow-Up of Subjects After Adverse Events*

If an AE/adverse reaction occurs, the Investigator will institute support and/or treatment as deemed appropriate. All SAEs ongoing at the time of the last visit or discontinuation from the study will be followed up until the AE/adverse reaction is resolved or stabilized, the subject is lost to follow-up, or there is other resolution to the event.

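### Protocol 8.3.1 gives opposite answers on whether a life-threatening or medically important event that is treated in an emergency room and released is an SAE

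*Protocol*

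**What the plan says.** Protocol 8.3.1 defines an SAE by a list of six outcomes, any one of which is enough in the view of either the investigator or the sponsor. Three entries matter here.

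- **Life-threatening.** The test is whether "its occurrence places the subject at immediate risk of death". Admission plays no part.
- **Hospitalization.** This is a separate entry: "Inpatient hospitalization or prolongation of existing hospitalization".
- **Medically important.** The explanatory paragraph below the list says: "Important medical events that may not result in death, be life-threatening, or require hospitalization may be considered serious when" medical judgment finds that they may jeopardize the subject and may need intervention to prevent a listed outcome.

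The paragraph after that takes two things out of the definition. The first is "Treatment on an outpatient emergency basis that does not result in hospital admission". The second is "a hospitalization that is elective or is a preplanned treatment for a pre-existing condition that is unrelated to the medication under study", and the sentence closes by requiring that the condition "has not worsened since the start of the study, is not considered an SAE".

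Protocol 7.2.1 gives this instruction about adverse events arising at home: "If the event is life-threatening, then the subject should go to the emergency room".

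The SAP has no SAE definition of its own. SAP 10.1 plans a table of serious TEAEs, and SAP 10.2.2 provides a column in the AE listing that marks SAEs. Both take the classification as it comes from the sites and the sponsor.

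**The concern.** The exclusion is worded as a rule about SAE status as a whole. It is not limited to the hospitalization entry, and it carries no proviso for an event that qualifies on another ground. An investigator who applies it literally could mark as non-serious an event that put the subject at immediate risk of death, because the subject was treated in an emergency room and sent home. The protocol itself directs life-threatening events to that setting.

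SAE status drives what happens next. Under Protocol 8.3.1 it triggers the SAE form, the report to the CRO within 24 hours, notification of the IRB by the investigator, and reporting to the FDA by the sponsor. It also decides whether the event appears in the serious TEAE table of SAP 10.1. SAP 7.4.2 plans no safety monitoring committee, so prompt individual SAE reports are an important route by which such an event would come to attention.

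**Working it through.** No arithmetic applies, and the plan states no figure on this point. The check is to put the list and the exclusion side by side and see whether they agree for each kind of event.

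| Event | Under the six-outcome list | Under the exclusion sentence | Do they agree? |
|---|---|---|---|
| Meets no criterion; emergency room, released | Not an SAE | Not an SAE | Yes |
| Emergency room, then admitted | SAE (hospitalization) | Does not apply | Yes |
| Life-threatening; emergency room, released | SAE | Not an SAE | **No** |
| Medically important on medical judgment; emergency room, released | SAE | Not an SAE | **No** |
| Death | SAE | Settled elsewhere: 8.3.1 separately requires every death during study and follow-up to be reported as an SAE | Yes |

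The conflict is confined to events that qualify on a ground other than hospitalization or death and are handled without admission.

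I then looked for text that would settle it.

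1. **The rest of the exclusion sentence.** The limiting conditions (pre-existing, unrelated, not worsened) attach, on an ordinary reading, to the elective or preplanned hospitalization. The outpatient emergency limb has no condition except the absence of admission.
2. **The medically important paragraph.** It says an event can be serious without hospitalization. That contradicts a literal reading of the exclusion but does not limit it. The protocol has no rule on which paragraph prevails.
3. **The paragraph separating severity from seriousness (8.3.1).** It says seriousness rests on outcome or action criteria. It does not mention the exclusion.
4. **The reporting paragraphs (8.3.1).** They apply to any SAE and so depend on the definition.
5. **SAP 10.1 and 10.2.2.** They tabulate and flag SAEs without redefining them.

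None of these confines the exclusion to the hospitalization entry.

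Last, what survives if an investigator follows the exclusion. Protocol 8.3 requires every AE after consent to be recorded whatever its cause, with seriousness among the documented items. SAP 10.1 puts all AEs in a by-subject listing. The event itself is therefore kept. Its serious flag and everything that depends on that flag may not be.

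**The case against.** The strongest reply is that the sentence makes sense as a gloss on the hospitalization entry. Both of its subjects are kinds of care: an emergency visit without admission, and a planned admission. Paired in this way, they most naturally say that neither counts by itself as a hospitalization that makes an event serious. On that reading there is no conflict, since a life-threatening event stays serious on its own ground. This is probably what was intended. But the text does not say it: the sentence ends by denying SAE status, not by denying that the hospitalization entry is met.

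A second reply is that the sponsor may also judge seriousness and could reclassify a recorded AE. That stands as a backstop. It is weaker than the primary route, because the 24-hour notice depends on the site first treating the event as an SAE, and the AE recording section (8.3) sets no comparable deadline for other events.

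Four stronger readings might be inferred. The documents support none of them.

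- **That serious events would go unreported altogether.** They would still be recorded and listed as AEs.
- **That the exclusion overrides the list because it comes later.** Paragraph order carries no stated precedence. The text gives two answers, not one wrong answer.
- **That fainting or shortness of breath would commonly fall into the gap.** Protocol 7.2.1 names these as reasons to contact the investigator; the emergency room instruction is a separate sentence about life-threatening events. The documents do not say how often such symptoms are managed without admission, and a faint that meets no criterion is properly not an SAE.
- **That the number of affected events can be estimated from earlier trials.** Protocol 2.2 reports no treatment-emergent SAE, with 168 patients exposed. The rule of three gives an upper 95% bound of 3/168 = 1.8%, or 0.018 × 80 = 1.4 among about 80 Nyxol subjects (half of 160). That bounds SAEs of any kind. It is not an expected count, and it says nothing about the much narrower set that is serious on another ground, treated and released, and then misclassified.

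**Conclusion.** The point holds as an internal contradiction in a reporting definition. For a life-threatening or medically important event treated in an emergency room without admission, Protocol 8.3.1 says both that it is an SAE and that it is not, and nothing else in the protocol or SAP resolves this. The consequence is that such an event may not be reported as an SAE, although it would remain in the AE data.

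No magnitude is claimed, because the documents give no rate for events of this kind; the number could be zero. The conclusion rests on the literal wording and on the possibility that some investigator applies it literally. It does not assume that the sponsor meant the exclusion to reach that far. No endpoint, efficacy analysis or analysis population is affected.

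**What to change.** Reconcile the two paragraphs by tying the exclusion to the hospitalization criterion only. For the outpatient emergency limb, replace the denial of SAE status with wording such as: *does not by itself meet the hospitalization criterion; an event that meets any other seriousness criterion above remains an SAE.* Carry the same wording into the SAE instructions given to sites, so that the form and the protocol agree.

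If the narrow reading was always intended, this only states it. The cost is one clause and at most a few extra SAE forms. The SAP needs no change, because its serious TEAE table and listing take the classification as given.
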